### **10.4.4 Supportive and Sensitivity analyses**

As a supportive analysis, ORR based on RECIST v1.1 criteria as per BICR will be analyzed with the same analysis conventions as the primary efficacy analysis, and the treatment effect will be summarized by the ORR with its 95% confidence interval using the Clopper-Pearson method.

As sensitivity analyses for ORR in the FAS, data from part 2 will be combined with data from part 1 to assess efficacy within the following sub-groups:

- LDH ( $\leq$  ULN vs.  $>$  ULN)
- ECOG PS (0 vs. 1 vs. 2)

## **10.5 Secondary objectives**

The secondary objectives in this study are to evaluate efficacy in terms of duration of response (DoR), progression-free survival (PFS), disease control rate (DCR), and overall survival (OS) of spartalizumab in combination with novel agents in patients with previously treated unresectable or metastatic melanoma. DOR, PFS, and DCR will be based on investigator assessment and a BICR process will be conducted as a supportive analysis.

### **10.5.1 Key secondary objective**

The key secondary objective is to determine duration of response treatment with spartalizumab in combination with novel agents in patients with previously treated unresectable or metastatic melanoma.

Duration of response (DOR) only applies to subjects whose best overall response is complete response (CR) or partial response (PR) according to RECIST v1.1, per local review.

The start date is the date of first documented response of CR or PR (i.e., the start date of response, not the date when response was confirmed), and the end date is defined as the date of the first documented progression or death due to underlying cancer. Subjects continuing without progression or death due to underlying cancer will be censored at the date of their last adequate tumor assessment. DOR will be listed and summarized by treatment group for all subjects in the FAS with confirmed best overall response (BOR) of CR or PR.

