### **Progression-free survival**

[figure not shown]
Progression-free survival (PFS) is defined as the interval of time (in months) between the date of randomization to the date of event defined as the first documented disease progression (according to RECIST v1.1 criteria) or death due to any cause (whichever comes first). If a subject has not had an event before leaving study or initiation of subsequent anti-cancer therapy, progression-free survival is censored at the date of last adequate tumor assessment. Censoring of subjects who have not had an event before initiation of subsequent anti-cancer therapy corresponds to option F(2) presented in [Table 14-9](#) in [Appendix 2](#) and is used in this study in order to obtain PFS estimates that are not confounded by subsequent therapies.

PFS based on RECIST v1.1 will be analyzed in the FAS population. The PFS distribution will be estimated using the Kaplan-Meier method, and the Kaplan-Meier curves, medians and 95% confidence intervals of the medians will be presented for each treatment group.

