**Table 14-9 Options for event dates used in PFS, TTP, duration of response**

Situation		Options for end-date (progression or censoring)  (1) = default unless specified differently in the protocol or RAP	Outcome
A	No baseline assessment	(1) Date of randomization/start of treatment 	Censored
B	Progression at or before next scheduled assessment	(1) Date of progression (2) Date of next scheduled assessment 	Progressed Progressed
C1	Progression or death after exactly one missing assessment	(1) Date of progression (or death) (2) Date of next scheduled assessment 	Progressed Progressed
C2	Progression or death after two or more missing assessments	(1) Date of last adequate assessment  (2) Date of next scheduled assessment  (3) Date of progression (or death)	Censored Progressed Progressed
D	No progression	(1) Date of last adequate assessment	Censored

Situation		Options for end-date (progression or censoring)  (1) = default unless specified differently in the protocol or RAP	Outcome
E	Treatment discontinuation due to 'Disease progression' without documented progression, i.e. clinical progression based on investigator claim	(1) Ignore clinical progression and follow situations above (2) Date of discontinuation (visit date at which clinical progression was determined)	As per above situations  Progressed
F	New anticancer therapy given	(1) Ignore the new anticancer therapy and follow situations above (ITT approach) (2) Date of last adequate assessment prior to new anticancer therapy (3) Date of secondary anti-cancer therapy (4) Date of secondary anti-cancer therapy	As per above situations Censored  Censored Event
G	Deaths due to reason other than deterioration of 'Study indication'	(1) Date of last adequate assessment	Censored (only TTP and duration of response)

1. =Definitions can be found in [Section 14.2.3.2.7](#)
2. =After the last adequate tumor assessment. "Date of next scheduled assessment" is defined in [Section 14.2.3.2.7](#).
3. =The rare exception to this is if the subject dies no later than the time of the second scheduled assessment as defined in the protocol in which case this is a PFS event at the date of death.

The primary analysis and the sensitivity analyses must be specified in the protocol. Clearly define if and why options (1) are not used for situations C, E and (if applicable) F.

[figure not shown]

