Situations C (C1 and C2): Progression or death after one or more missing assessments: The primary analysis is usually using options (1) for situations C1 and C2, i.e.

- (C1) taking the actual progression or death date, in the case of only one missing assessment.
- (C2) censoring at the date of the last adequate assessment, in the case of two or more consecutive missing assessments.

In the case of two or missing assessments (situation C2), option (3) may be considered jointly with option (1) in situation C1 as sensitivity analysis. A variant of this sensitivity analysis consists of backdating the date of event to the next scheduled assessment as proposed with option (2) in situations C1 and C2.

**Situation E: Treatment discontinuation due to 'Disease progression' without documented progression:** By default, option (1) is used for situation E as subjects without documented PD should be followed for progression after discontinuation of treatment. However, option (2) may be used as sensitivity analysis. If progression is claimed based on clinical deterioration instead of tumor assessment by e.g. CT-scan, option (2) may be used for indications with high early progression rate or difficulties to assess the tumor due to clinical deterioration.

**Situation F: New cancer therapy given:** the handling of this situation must be specified in detail in the protocol. However, option (1) (ITT) is the recommended approach; events documented after the initiation of new cancer therapy will be considered for the primary analysis i.e. progressions and deaths documented after the initiation of new cancer therapy

would be included as events. This will require continued follow-up for progression after the start of the new cancer therapy. In such cases, it is recommended that an additional sensitivity analysis be performed by censoring at last adequate assessment prior to initiation of new cancer therapy.

Option (2), i.e. censoring at last adequate assessment may be used as a sensitivity analysis. If a high censoring rate due to start of new cancer therapy is expected, a window of approximately 8 weeks performed after the start of new cancer therapy can be used to calculate the date of the event or censoring. This should be clearly specified in the analysis plan.

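### Duration of response censors deaths not attributed to the melanoma, while PFS counts every death, so the key secondary endpoint can look longer than it was

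*Protocol*

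**What the plan says.** Section 10.5.1 defines DoR for confirmed responders from the first documented response, and "the end date is defined as the date of the first documented progression or death due to underlying cancer". Everyone else is censored: "Subjects continuing without progression or death due to underlying cancer will be censored at the date of their last adequate tumor assessment".

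Appendix 2 agrees. Section 14.2.3.2.5 gives DoR the same end date and censoring as time to progression, which in Section 14.2.3.2.3 counts only cancer deaths. Table 14-9, situation G, lists deaths from other reasons with the outcome "Censored (only TTP and duration of response").

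PFS in Section 10.5.2 is different: its event is progression "or death due to any cause (whichever comes first").

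On subsequent anti-cancer therapy, Section 10.5.2 chooses option F(2) for PFS, censoring at the last adequate assessment, which "is used in this study in order to obtain PFS estimates that are not confounded by subsequent therapies". Section 10.5.1 makes no choice for DoR. Table 14-9 covers PFS, time to progression and DoR, and its first option for situation F is "1) Ignore the new anticancer therapy and follow situations above (ITT approach"). The table heading explains "(1) = default unless specified differently in the protocol or RAP". The text on situation F below the table says "the handling of this situation must be specified in detail in the protocol" and recommends option (1).

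**The concern.** Death ends a response whatever its cause. Censoring it treats a responder killed by toxicity as exchangeable with responders still alive and in response, which makes the estimate more favourable exactly where the treatment does harm. It also makes the endpoint depend on the reason recorded for death (study indication or other, Section 14.2.3.2.2), in an open-label study read locally.

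DoR carries weight here. It is the key secondary endpoint (Table 3-1) supporting a response rate with no comparator arm. Sections 10.4.2.1 and 10.4.2.2 single it out among the data considered for expansion, and Section 4.3 times the primary analysis to allow six months of response. With the two definitions as written, a responder who dies of a non-cancer cause before any new therapy would normally be a PFS event and a DoR censoring.

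**Working it through.** **No stated figure to reproduce.** The protocol gives no DoR median, rate or power (Section 10.9 marks power for key secondary variables as not applicable). The check is a comparison of rules plus illustrations on assumed inputs.

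**1. The rules side by side**

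| Situation in a responder | DoR | PFS |
|---|---|---|
| Documented progression | event | event |
| Death from the melanoma | event | event |
| Death from another cause, including toxicity | censored at last adequate assessment (10.5.1; situation G) | event (10.5.2) |
| New anti-cancer therapy before progression | not stated in 10.5.1; F(1) by default | censored, F(2) (10.5.2) |

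**2. Direction of the death rule.** A death counted as an event multiplies the Kaplan-Meier curve by (n − 1)/n at that time, where n is the number at risk. A censored death applies no such factor. Backdating the censoring to the last adequate assessment also shrinks the risk set a little earlier, so the censored version can dip slightly below the other between that assessment and the death. From the death onward it is never lower.

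**3. Landmark illustration.** Assumed: 25 responders (25% of the 100 planned in arm 1A), 8 progressions and 2 non-cancer deaths by month 6, no other censoring.

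- Deaths counted: (25 − 8 − 2)/25 = 15/25 = 60%.
- Deaths censored before any progression: 23 at risk and 8 progress, so 15/23 = 65.2%.
- Deaths censored after all progressions: (25 − 8)/25 = 17/25 = 68%.

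The difference is 5.2 to 8 percentage points for two deaths, or 2.6 to 4 per death. Backdated censoring pulls towards the lower end.

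**4. Median illustration.** Assume constant hazards and let s be the share of all progression-or-death events that are non-cancer deaths. The protocol gives no value for s, so 0 to 20% is assumed. Median with those deaths censored = median counting all deaths / (1 − s).

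| s | True median 6 months | True median 12 months |
|---|---|---|
| 0 | 6.0 | 12.0 |
| 5% | 6.3 | 12.6 |
| 10% | 6.7 | 13.3 |
| 20% | 7.5 | 15.0 |

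**5. Subsequent therapy: F(1) against F(2).** Large-sample simulation with a 9-month median on study treatment and new therapy started at half the progression hazard (all assumed):

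| Hazard after new therapy | F(1) median | F(2) median |
|---|---|---|
| halved | 9.9 | 9.0 |
| unchanged | 9.0 | 9.0 |
| tripled (patients switched while failing) | 7.5 | 9.0 |

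F(1) can lengthen, leave or shorten DoR relative to F(2).

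**The case against.** The strongest reply is that the death rule is deliberate and consistent. Section 10.5.1, Sections 14.2.3.2.3 and 14.2.3.2.5, situation G and the censoring reasons in Section 14.2.4.5.6 all describe the same time-to-progression type of DoR. Non-cancer deaths still count in PFS and OS, and all deaths are summarised under safety. DoR is descriptive, with no hypothesis test. All of this stands: the definition is disclosed and the passages do not contradict each other. It does not remove the one-sided effect on the curve or the reliance on attributed cause of death.

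Two stronger readings are tempting but unsupported.

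- A reader might infer that DoR also runs through subsequent therapy, so that both rules lengthen it. Section 10.5.1 is silent. F(1) applies only by default, unless the protocol or analysis plan says otherwise, and the analysis plan is not at hand. Section 14.2.4.5.6 lists the start of subsequent therapy as a possible censoring reason for PFS and time to progression, and hence for DoR. F(1) is also the approach that Appendix 2 recommends, and its effect has no fixed direction. What remains is an option left unstated for DoR although Appendix 2 requires the protocol to state it.
- A reader might take the fatal multiple organ dysfunction in one of the first 35 arm 1 subjects (Section 2.4.1.1) as evidence that the bias has already occurred. That section does not call the event immune-related and does not say that the subject was a responder. The general statement on fatal events in Section 2.6.1 concerns checkpoint inhibitors as a class.

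**Conclusion.** The concern holds for the death rule. DoR censors non-cancer deaths, toxicity deaths included, that PFS counts, and from such a death onward this can only leave the Kaplan-Meier DoR unchanged or raise it. With the assumed 25 responders, 8 progressions and 2 such deaths by month 6, the reported figure would be 65.2% to 68% instead of 60%. With a non-cancer share of 0 to 20%, the median would be inflated by 0 to 25%. All these inputs are assumptions. The effect is nil if no responder dies of a non-cancer cause, and the formal ORR test and its error rate are unaffected.

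The documents support saying that DoR can be overstated. They do not show that it is. The unstated handling of subsequent therapy is a separate clarification, not a second source of upward bias.

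**What to change.** 1. In Section 10.5.1, define the DoR event as first documented progression or death from any cause.
2. Keep the present cancer-death-only definition as a named sensitivity analysis.
3. Align Section 14.2.3.2.5 and Table 14-9, situation G, so that censoring of non-cancer deaths no longer governs the main DoR analysis.
4. As a clarification, state in Section 10.5.1 which situation F option applies to DoR: F(2) to match PFS, or F(1) with a reason for the difference.

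The cost is a few sentences and a programming flag. No extra data are needed: death dates are already collected, and Section 7.2.1.2 asks for scans to continue after new therapy where possible. The reported DoR may become slightly less favourable.

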### **10.5.2 Other secondary efficacy objectives**

All secondary efficacy endpoints according to RECIST v1.1 will be based on tumor assessments as per local assessment.

### **Progression-free survival**

[figure not shown]
Progression-free survival (PFS) is defined as the interval of time (in months) between the date of randomization to the date of event defined as the first documented disease progression (according to RECIST v1.1 criteria) or death due to any cause (whichever comes first). If a subject has not had an event before leaving study or initiation of subsequent anti-cancer therapy, progression-free survival is censored at the date of last adequate tumor assessment. Censoring of subjects who have not had an event before initiation of subsequent anti-cancer therapy corresponds to option F(2) presented in [Table 14-9](#) in [Appendix 2](#) and is used in this study in order to obtain PFS estimates that are not confounded by subsequent therapies.

PFS based on RECIST v1.1 will be analyzed in the FAS population. The PFS distribution will be estimated using the Kaplan-Meier method, and the Kaplan-Meier curves, medians and 95% confidence intervals of the medians will be presented for each treatment group.

### **Disease Control Rate**

Disease control rate (DCR) is defined as the proportion of subjects with best overall response of CR, PR, or SD according to RECIST v1.1 criteria and as per local review.

DCR will be calculated based on the FAS. DCR and its 95% confidence interval will be presented for each treatment group.

## **Overall Survival**

Overall survival (OS) is defined as the time from date of randomization to date of death due to any cause. If a subject is not known to have died, then OS will be censored at the latest date the subject was known to be alive (on or before the cut-off date).

OS will be analyzed in the FAS population. The OS distribution will be estimated using the Kaplan-Meier method, and the Kaplan-Meier curves, medians and 95% confidence intervals of the medians will be presented for each treatment group.

### **10.5.3 Safety objectives**

#### **10.5.3.1 Analysis set and grouping for the analyses**

For all safety analyses, the safety set will be used. All listings and tables will be presented by treatment group. In addition, pooled safety analysis based on all subjects will be produced.

The overall observation period will be divided into three mutually exclusive segments:

1. pre-treatment period: from day of subject's informed consent to the day before first dose of study medication
2. on-treatment period: from day of first dose of study medication to 30 days after last dose of study medication
3. post-treatment period: starting at day 31 after last dose of study medication.

If dates are incomplete in a way that clear assignment to pre-, on-, or post-treatment period cannot be made, then the respective data will be assigned to the on-treatment period. Additional details to address incomplete AE and/or dosing dates will be addressed in the SAP.

Additional summaries will be displayed to report deaths, all AE, AE related to study treatment, all SAE and SAE related to study treatment collected up to 150 days after last administration of spartalizumab.

Safety will be assessed based on all treated subjects; toxicities will be defined by CTCAE v5. Incidence and severity of adverse events, causality attribution to drug, time to event onset, duration of the event, its resolution and concomitant medications administered will be recorded. Additional safety assessments will include laboratory safety assessment, vital signs, and cardiac assessment.

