### 6.1.1 Dosing regimen

After randomization/enrollment, subjects will receive the study treatment corresponding to the arm they were randomized/enrolled into as per the dose and schedule of administration defined in [Table 6-1](#) for each investigational drug.

Patient must start study treatment within 3 days after randomization/enrollment.

Each treatment cycle is 28 days.

In-clinic intravenous infusions and s.c. injections of investigational drugs must be scheduled according to the appropriate number of calendar days from the day of first study treatment administration on C1D1.

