### 6.3.1.2 Maximum duration of study drug(s) interruption

If the treatment with spartalizumab is interrupted for more than 12 weeks (counted from the time the AE reaches a grade that leads to spartalizumab interruption), spartalizumab must be permanently discontinued.

If the treatment with LAG525 is interrupted for more than 12 weeks (counted from the time the AE reaches a grade that leads to LAG525 interruption), LAG525 must be permanently discontinued.

If the treatment with capmatinib is interrupted for more than 3 consecutive weeks (counting from the first day when a dose was interrupted), then capmatinib must be permanently discontinued.

If the treatment with ribociclib is interrupted for more than 28 consecutive days due to ribociclib-related toxicity (counting from the first day when a dose was interrupted, including the 7 days of planned interruption of dosing between Day 22-28 of a cycle), then ribociclib must be permanently discontinued.

If the treatment with canakinumab is interrupted for more than 4 weeks (counted from the intended day of the next scheduled dose), canakinumab must be permanently discontinued.

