### 6.3.1.3.2 Dose modification for potential immune-mediated adverse events (irAEs)

Adverse events of special interest include irAEs that are associated with spartalizumab/LAG525 treatment. An irAE may be experienced by subjects treated with spartalizumab or/and LAG525 due to their mechanism of action and predicted based on the reported experience with other checkpoint inhibitors that have a similar mechanism of action. Investigators must be vigilant and carefully identify AEs that may be suggestive of potential irAEs as their appearance may be sub-clinical and early diagnosis is critical for adequate management and resolution.

Immune-related adverse events may be of low grade and self-limited, most frequently involving the gastrointestinal tract (e.g. diarrhea/colitis), skin (e.g. rashes, pruritus), liver (e.g. hepatitis), lung (e.g. pneumonitis), kidneys (e.g. nephritis) and endocrine systems (e.g. hypothyroidism, hyperthyroidism, type I diabetes, hypophysitis including hypopituitarism and adrenal insufficiency). Other immune-related AEs may rarely include the nervous system (e.g. encephalitis, Guillain-Barre syndrome, myasthenia gravis), eye (e.g. uveitis, vision changes), musculo-skeletal system (e.g. myositis, arthritis), pancreas (e.g. pancreatitis), cardio-vascular system (e.g. vasculitis, myocarditis) or blood system (e.g. anemia, cytopenias), and severe skin reactions such as toxic epidermal necrolysis or Stevens-Johnson syndrome. Furthermore, complications in patients with bone marrow or solid organ transplant have been reported (e.g. organ rejection, severe graft-versus-host disease). However, nearly all organs can be affected by immune-mediated toxicities. IrAEs often occur relatively early (mostly within weeks to 3 months after treatment initiation), however, may develop at any time during treatment (even after several months), and may also occur after treatment discontinuation. Serological, immunological and histological assessments should be performed as deemed appropriate by the investigator, to verify the potential immune-mediated nature of the AE, and exclude neoplastic, infectious or metabolic origin of the AE.

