**Table 7-1 Allowable visit windows**

Visit name	Assessments	Window allowed
Screening	Physical examination (complete), Performance Status, weight, vital signs, hematology, chemistry, coagulation	≤ 14 days before C1D1
	Serum pregnancy test	≤ 72 hours before C1D1
	For Arm 1A: Collection/submission of newly or recently obtained baseline tumor biopsy sample (as defined in Section 7.2.3.1.1 ) for LAG-3 status central assessment	≤ 35 days before enrollment (tumor sample should be submitted as early as possible and at the latest 20 days prior to planned enrollment date to allow sufficient time for central testing)
	Other screening assessments	≤ 28 days before C1D1
C1D1	Administration of first dose of study treatment	Maximum 3 days after date of randomization/enrollment
	All visit assessments	NA (if screening laboratory assessments and physical examination were performed ≤ 72 hours before first dose of study treatment, they do not need to be repeated on C1D1)
Day 1 visit of all subsequent cycles	All visit assessments (except tumor assessment)	± 4 days
	Administration of i.v. and s.c. investigational drugs	± 4 days

Visit name	Assessments	Window allowed
During Treatment and Efficacy follow-up periods	Tumor assessments	± 7 days
EoT	All assessments	+ 7 days after the discontinuation of the last study drug (i.e. within 7 days after the last dose of the last study drug or after the date when decision was made to permanently discontinue both study drugs/the last study drug) (tumor assessments do not need to be repeated if performed within 30 days prior to last study treatment administration)
30-day safety follow-up visit	All assessments	30 days (+ 7 days) after last dose of study treatment (if last dose was more than 30 days ago when the decision is taken to discontinue study treatment, then 30-day safety follow-up to be performed as soon as possible)
60-, 90-, 120-Day follow-up phone call/onsite visit	All assessments	± 7 days
150-Day follow-up visit	All assessments	+ 14 Days
Survival follow up	All assessments	± 14 days

[figure not shown]

	Category	Protocol section	Screening period	Treatment Period (Cycle = 28 days)										Follow-up (FU) Period						Survival				
			Screening	Cycle 1			Cycle 2			Cycle 3				Subsequent Cycles Day 1	End of Treatment (EoT)	Safety FU					Efficacy FU (Not applicable if EoT due to progression)	End of post-treatment FU		

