#### **10.5.3.2 Adverse events**

Summary tables for AE will include only AE that started or worsened during the on-treatment period, the treatment-emergent AE.

The incidence of treatment-emergent adverse events (new or worsening from baseline) will be summarized by system organ class and or preferred term, severity (based on CTCAE v5 grades), type of adverse event, and relation to study treatment

Serious adverse events, non-serious adverse events and adverse events of special interest (AESI) during the on-treatment period will be tabulated. The list of AESI will also include relevant events for spartalizumab, LAG525, capmatinib, canakinumab and ribociclib which will be defined in the SAP.

Project-specific AESI should be defined in the case retrieval strategy (CRS) with regular updates whenever necessary.

All deaths (on-treatment and post-treatment) will be summarized.

All AE, deaths and serious adverse events (including those from the pre and post-treatment periods) will be listed and those collected during the pre-treatment and post-treatment period will be flagged.

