### **10.5.3.3 Laboratory abnormalities**

Grading of laboratory values will be assigned programmatically as per NCI Common Terminology Criteria for Adverse Events (CTCAE) v5. The calculation of CTCAE grades will be based on the observed laboratory values only, clinical assessments will not be taken into account.

CTCAE Grade 0 will be assigned for all non-missing values not graded as 1 or higher. Grade 5 will not be used.

For laboratory tests where grades are not defined by CTCAE v5, results will be categorized as low/normal/high based on laboratory normal ranges.

The following summaries will be generated separately for hematology, and biochemistry tests:

- Listing of all laboratory data with values flagged to show the corresponding CTCAE v5 grades if applicable and the classifications relative to the laboratory normal ranges

For laboratory tests where grades are defined by CTCAE v5

- Worst post-baseline CTCAE grade (regardless of the baseline status). Each subject will be counted only once for the worst grade observed post-baseline.
- Shift tables using CTCAE v5 grades to compare baseline to the worst on-treatment value

For laboratory tests where grades are not defined by CTCAE v5

- Shift tables using the low/normal/high/ (low and high) classification to compare baseline to the worst on-treatment value.

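### AESIs, AESI worsenings and laboratory peaks dated more than 30 days after a final dose fall outside the AESI and laboratory shift tables, although the trial's own visit windows and dose holds run past day 30

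*Protocol*

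**What the plan says.** Protocol Section 10.5.3.1 divides observation into three exclusive segments. The second is the "on-treatment period: from day of first dose of study medication to 30 days after last dose of study medication" and the third is the "post-treatment period: starting at day 31 after last dose of study medication". The clock runs from the last dose actually given, not from the decision to stop.

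Three rules build on this:

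- **AESI (Section 10.5.3.2):** "adverse events of special interest (AESI) during the on-treatment period will be tabulated". The list of AESI is left to the SAP, but the period is fixed here.
- **Laboratory data (Section 10.5.3.3):** "Shift tables using CTCAE v5 grades to compare baseline to the worst on-treatment value". The low/normal/high shift tables for ungraded tests carry the same limit. A separate table gives the worst post-baseline CTCAE grade and states no on-treatment limit.
- **Extra summaries (Section 10.5.3.1):** deaths, all AEs, related AEs, all SAEs and related SAEs are summarised up to 150 days after the last spartalizumab dose. AESI and laboratory data are not named.

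Elsewhere the protocol allows for treatment ending later than day 30. Table 7-1 provides for the case "if last dose was more than 30 days ago when the decision is taken to discontinue study treatment". Section 6.3.1.2 makes discontinuation mandatory only "If the treatment with LAG525 is interrupted for more than 12 weeks", with the same limit for spartalizumab and 4 weeks for canakinumab. Section 6.3.1.3.2 counts immune-related events among the AESI and says that they "may also occur after treatment discontinuation".

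**The concern.** A 30-day window after the last dose suits a drug taken daily or weekly. Here the dosing interval alone is 28 days plus a visit window, so the window closes at about the time when the next dose is due. Any hold that never resumes then lies largely outside it. The visit rules were adapted to a late stop decision, but the analysis window was not.

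At stake is the table a reader will use for immune-related toxicity of the antibody combinations. Late-onset immune-related events, and worsenings during a hold or a steroid taper, are collected but never tabulated as AESI. The shift table is also the only laboratory table that relates the worst grade to baseline. Eligibility admits AST and ALT up to 5 x ULN in subjects with liver metastases (Section 5.2.2), so the worst post-baseline grade table, which ignores baseline status, cannot replace it. Arm 1A is the arm most exposed: Section 4.1.1 records all four randomized arms as futile, so arm 1A is the one still to enroll.

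**Working it through.** The check is calendar arithmetic on the protocol's own intervals. The protocol gives no figure of its own to reproduce.

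**Inputs**

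- On-treatment window: 30 days after the last dose (Section 10.5.3.1).
- Cycle: "Each treatment cycle is 28 days" (Section 6.1.1). Day 1 visit and dosing window: plus or minus 4 days (Table 7-1).
- End of Treatment visit: up to 7 days after the last dose or after the stop decision (Section 7.1.5).
- Hold limits (Section 6.3.1.2): 12 weeks = 84 days for spartalizumab and LAG525, counted from when the AE reaches the interrupting grade; 4 weeks for canakinumab, counted from the intended next dose.

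**Days after the last infusion or injection, arms 1, 1A and 3**

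| Event | Formula | Day |
|---|---|---|
| Next-cycle visit, previous dose on schedule | 28 - 4 to 28 + 4 | 24 to 32 |
| Same, previous dose 4 days early | 28 + 4 + 4 | 36 |
| End of Treatment samples, decision at an on-time visit | 28 + 7 | up to 35 |
| End of Treatment samples, decision at a late visit | 32 + 7 | up to 39 |
| Visit after one missed dose | 56 - 4 to 56 + 4 | 52 to 60 |
| 12-week limit, interrupting grade reached on day 0 to 32 | 0 + 84 to 32 + 84 | 84 to 116 |
| Canakinumab limit | 28 + 28 | 56 |

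Every row except the early part of the first passes day 30. For an unresumed 12-week hold, the days outside the window run from 84 - 30 = 54 (grade reached on day 0) to all 84 (grade reached on day 30 or later).

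**Arms 2 and 4**

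The window runs from the last dose of any study drug. With ribociclib taken to day 21 of the cycle (20 days after the infusion) it closes on day 20 + 30 = 50. With capmatinib taken to day 28 (27 days after) it closes on day 27 + 30 = 57. A day-32 visit is inside both. The gap opens only if the oral drug was stopped earlier.

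**What leaves which table**

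- An AE is placed by the date on which it started or worsened. A worsening is a second dated record (Section 8.1.1). One dated day 31 or later with no further dose is post-treatment, so it is not in the AESI table.
- The same holds for a laboratory value and the shift tables.
- If dosing resumes, the last dose moves forward and the whole hold becomes on-treatment.

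**Would the 150-day summaries reach far enough?** The latest hold limit above plus the End of Treatment window is 116 + 7 = day 123, inside 150.

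**The case against.** The strongest reply is that the protocol deliberately pairs a 30-day window with 150-day summaries, and that nothing in it is contradictory. An AESI is an AE, so a late immune-related event is in the 150-day all-AE summary and in the flagged listings. Late peaks in CTCAE-graded tests are in the worst post-baseline grade table and the laboratory listing. These are descriptive tables on which no test or decision threshold depends. All of this stands, and it confines the loss to two sets of tables. It does not close the gap: the 150-day summary does not identify AESI, and for tests without CTCAE grades the listing is the only place where a late peak appears.

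It can also be said that AESI groupings are SAP detail. That holds for the list of terms. The period is fixed in the protocol.

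A reader might infer more than the documents support:

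- **That AESIs which end treatment disappear.** An AESI that causes the next dose to be withheld has normally started by day 30. It stays in the table even if discontinuation follows 12 weeks later. What can go missing is a new AESI or a later worsening.
- **That a late visit moves AEs out.** AEs carry their own onset dates, so the day-31 and day-32 visits mainly affect laboratory samples.
- **That the intervals give a percentage lost.** They count calendar days under chosen scenarios. The protocol gives neither the distribution of visit days nor the frequency of unresumed holds, so no share of events follows.

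**Conclusion.** The point holds in a narrow form. New AESIs, worsenings of AESIs and laboratory peaks dated day 31 or later after a last dose that is not followed by another are absent from the AESI tables and the laboratory shift tables. This concerns mainly arms 1, 1A and 3. It rests on the wording of Sections 10.5.3.1 to 10.5.3.3 and assumes that dosing does not resume.

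The direction is toward fewer reported AESIs and milder shifts, but the size cannot be stated from the protocol. The documents do not support a claim that the overall safety profile is materially understated, because the all-AE, SAE and worst-grade summaries still hold most of this information. This is a worthwhile, inexpensive improvement rather than a defect that threatens the trial's conclusions.

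**What to change.** - In Section 10.5.3.1, add AESI to the summaries produced up to 150 days after the last administration of spartalizumab, and cross-refer to this in Section 10.5.3.2.
- In Section 10.5.3.3, let both kinds of shift table include values up to the later of 30 days after the last dose or the End of Treatment visit. Where no End of Treatment visit took place, the 30-day limit stays.

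The main 30-day AE tables can remain as they are. The cost is wording in three subsections and one more AESI table, from data already collected. A few events unrelated to drug may enter, and the end of the laboratory window will vary between subjects with the date of the End of Treatment visit. A footnote to the shift tables should say so.
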